#### K. Statistical Analysis Plan

Preliminary evaluation of participants' response to the interventions will be examined using quantitative data. While evaluation of outcomes is more appropriate for a fully-powered R01, we will examine variance and effect sizes of key outcomes from pre- to post-intervention, as well as post-intervention to 3-month follow-up using non-parametric tests and confidence intervals. The randomized trial is powered to detect an average estimated effect size equivalent to Cohen's  $d$  of 0.50 with the minimum sample size of 96 participants (i.e., 48 children, 48 parents). Analyses will explore potential patterns related to attrition. Every effort will be made to collect follow-up data from all participants, regardless of whether they completed the intervention.

L. Research references:

3. Lichter DT. Immigration and the New Racial Diversity in Rural America. *Rural Sociol*. 2012;77(1):3-35.
5. Tuñón-Pablos E, J D. Risk Factors for Overweight and Obesity among Mexican Children in New York. *International Journal of Population Research*. 2016.

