## 2. Sample size:

For Aim 1a: we will conduct a focus group with 6 promotoras (community health workers)

For Aim 1b: we will conduct two focus groups with a total of 20 (max) Latina mothers of 8- to 12-year-old children who are overweight or obese (85th BMI percentile)

For Aim 1c: we will conduct focus groups using one cohort of mothers and their children meeting eligibility to further refine the ADAPT manual. Parents and children will attend all six sessions of ADAPT+ sessions and provide feedback for manual optimization. Latina meal preparers in the family (primarily mothers) and their 8- to 12-year-old children (up to 10 children) will participate.

Summary of Participants 6 community health workers (promotoras or group facilitators); 30 Latina mothers (Aims 1a and b) 10 children (Aim 1c); Total = up to 46 participants (non-clinical trial portions of the project)/

Aim 2: A small pilot RCT will be conducted (clinical trial). There will be cohorts of 8-10 child/parent pairs at each site (2 sites), and 3 intervention cycles. Estimating that all cohorts are the minimum of 8 pairs, we will have a total minimum target sample size of 48 pairs, or 96 total participants (48 parents and 48 youth). If all groups are the maximum of 10 pairs, we will have a maximum total sample size of 60 pairs, or 120 total participants (60 parents and 60 youth). We

aim for a minimum of 48 pairs with a possible range of 48 to 60 pairs based on our study design. Starting in Year 2, in total we will run 3 ADAPT+ and 3 EUC cohorts.

D. Study Population inclusion and exclusion criteria;

C.3.2. Eligibility criteria. Promotoras trained to conduct focus groups by our study site partner, HSC, will identify families living in our target community meeting our eligibility criteria:

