1. Latino families with a child between the ages of 8 and 12; Note: pre-adolescents are targeted as this is a developmentally critical age group in terms of developing health-behavior skills and is an age group identified as in need of further study in the Latino population. 2. Child with a BMI %ile of 85 or higher; and 3. The target parent is at least 18 years old, is the main meal preparer, speaks and reads Spanish at a minimum of a 4th grade reading level (able to follow basic instructions in Spanish), and able to perform simple physical exercises. Although both parents and/or other caregivers can participate in the group, only data from the primary parent (main meal preparer) will be used for analyses. The parent is ineligible if he/she is non-ambulatory, is pregnant, or has a medical condition that may be negatively impacted by PA. A child who has a medical/developmental condition that precludes weight loss using conventional diet and PA methods or has been on antibiotics or steroids in the previous three months is also ineligible.

E. The expected results of the research, such as reports, papers, and contributions to theory;

We posit that mindfulness can improve intervention engagement (increasing receptiveness), which are demonstrated critical barriers to Latino families participating in childhood obesity interventions, by simultaneously reducing stress and enhancing the learning process around eating and PA. ADAPT plus mindfulness parent stress reduction to increase healthy eating and PA lifestyle behaviors in both parents and their children.

F. Name of the Principal Investigator and Faculty Advisor if applicable;

[name]

G. Any potential risks to the subjects;

This research is considered to be minimal risk. That means that the risks associated with this study are the same as what the participant would face every day. There are no known additional risks to those who take part in this study.

H. Any experimental procedures or interventions that will be implemented;

The study will assess acceptability of the integration of mindfulness parenting stress reduction into Adaptando Dieta y Acción Para Todos (ADAPT) to increase healthy lifestyle behaviors by: conducting a series of focus groups with our community health facilitators/ promotoras and parents of children (8-12 years old) with obesity to obtain feedback about and refine each of our 6 integrated sessions and evaluate optimization of ADAPT+ sessions.

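### The power claim for d = 0.50 names no contrast, alpha or power level; read as a comparison of arms, power at the 48-pair minimum is about 40% (assuming two-sided alpha 0.05, no baseline adjustment)

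*Combined protocol and SAP*

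**What the plan says.** The claim is one sentence in section K (Statistical Analysis Plan). It begins "The randomized trial is powered to detect an average estimated effect size equivalent to Cohen's". The value that it then gives for d, and the sample to which it ties that value, read "of 0.50 with the minimum sample size of 96 participants (i.e., 48 children, 48 parents"). No alpha, sidedness, power level, outcome, test or contrast is attached to it, and no other section supplies them.

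The sentence before it opens with a caveat, "While evaluation of outcomes is more appropriate for a fully-powered R01", and then describes the analysis: "we will examine variance and effect sizes of key outcomes from pre- to post-intervention, as well as post-intervention to 3-month follow-up". The methods named for this are given only as "using non-parametric tests and confidence intervals". These are changes over time; no between-arm test is named.

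Section C, item 2 (Sample size) gives the numbers. At 8 pairs per cohort, "we will have a total minimum target sample size of 48 pairs, or 96 total participants (48 parents and 48 youth"). At 10 pairs per cohort, "we will have a maximum total sample size of 60 pairs, or 120 total participants (60 parents and 60 youth"). The same item plans three ADAPT+ and three EUC cohorts, and section H assigns whole cohorts to a condition. Section B lists child and parent measures separately; the Perceived Stress Scale, for example, is completed by parents only. Section D adds that "only data from the primary parent (main meal preparer) will be used for analyses".

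**The concern.** A power statement can be checked only if the contrast, test, alpha and power level are known, and none is given here. Because the sentence is about the randomized trial, and Aim 2 sets ADAPT+ against EUC, many readers will take it as power for a comparison of arms. The 96 then looks too large: it adds parents to children, whereas a parent outcome or a child outcome has at most one person per pair. That the 96 was used in this way is an inference, since no calculation is shown.

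This is the only power figure in the document. A reader who takes it at face value could treat a null difference between arms as informative about d = 0.50, or could carry the figure into planning of the larger trial.

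**Working it through.** **The plan's own figure.** It cannot be reproduced, because alpha, power level and contrast are missing. What can be done is to compute power under each plausible reading.

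**Inputs from the document.** d = 0.50 (section K). Minimum sample: 3 cohorts per arm × 8 pairs = 24 pairs per arm. Maximum: 3 × 10 = 30 pairs per arm (section C, item 2). One parent and one child per pair, measured separately (sections B and D), so n = 24 or 30 per arm for any one outcome.

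**Assumed, because not stated.** Alpha 0.05, shown two-sided and one-sided; 80% power as the benchmark.

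**1. Between arms, unadjusted, cohorts ignored.** Two-sample t-test, noncentrality d × √(n/2), 2n − 2 degrees of freedom. For n = 24 the noncentrality is 0.50 × √12 = 1.73.

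| People per arm | Power, two-sided | Power, one-sided | d for 80%, two-sided |
|---|---|---|---|
| 24 (minimum) | 39.6% | 52.5% | 0.83 |
| 30 (maximum) | 47.8% | 60.6% | 0.74 |
| 48 (all 96 people counted as independent) | 67.9% | 78.4% | 0.58 |

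Reaching 80% at d = 0.50 takes 64 per arm two-sided (80.1%) or 51 one-sided (80.6%). A rank-sum test at 24 per arm has about 38% power two-sided.

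**2. Parent and child averaged within a pair.** With 24 pairs per arm and within-pair correlation ρ, the variance is multiplied by (1 + ρ)/2. Two-sided power is 67% at ρ = 0 and falls to 47% at an assumed ρ = 0.6.

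**3. Baseline adjustment (not planned in section K).** With one follow-up and baseline-outcome correlation r, the residual variance is multiplied by 1 − r², so d becomes 0.50/√(1 − r²). The values of r are assumed; power is two-sided.

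| r | Adjusted d | 24 per arm | 48 per arm (96 independent) |
|---|---|---|---|
| 0.5 | 0.58 | 50% | 79.9% |
| 0.7 | 0.70 | 66% | 92% |
| 0.8 | 0.83 | 81% | 98% |

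So 80% needs r of about 0.80 with 24 per arm, or about 0.50 if all 96 people are treated as independent. Averaging both follow-ups, with all correlations equal, lowers the requirement at 24 per arm to about 0.70.

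**4. Pre-post change.** One-sample t-test, noncentrality d × √n, with d in SD-of-change units. Pooled over both arms, n = 48 of one role: 0.50 × √48 = 3.46, power 92%. If d is instead in raw SD units, it is divided by √(2(1 − r)); for r from 0.3 to 0.7, power is 82% to 99%. Within one arm of 24, the SD-of-change figure is 65%, and the raw-SD range is 51% to 86%.

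**5. Cohorts and attrition (illustrations only).** One possible cohort-level analysis compares six cohort means on 4 degrees of freedom, with variance 2(ICC + (1 − ICC)/8)/3. It gives 27% at ICC 0 and 21% at an assumed ICC of 0.05. Assumed attrition of 10% to 30% moves the 40% to 36% to 29%. The documents give neither an ICC nor an attrition rate, and the SAP does not name this cohort analysis.

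**The case against.** The strongest reply is that no comparison of arms was meant. The sentence just before the claim names only changes over time. The sentence itself gives 48 children and 48 parents, and 48 people of one role have 92% power for a pre-post change of d = 0.50. The phrase naming the randomized trial may serve only to separate Aim 2 from the focus groups of Aim 1. The outcomes that Aim 2 explicitly compares with EUC are attrition and satisfaction, while the eating, activity and stress measures are merely expected to respond to the intervention.

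This stands as a possible reading, and for that reason the documents do not show that the claim is false. A reader might infer from the 40% that the sponsor's calculation is wrong; that goes too far, because the calculation is not shown and one reading supports the figure. But a pooled pre-post test compares no randomized arms, so on that reading the sentence still needs rewording.

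A reader might also infer that even 96 independent people could not reach 80%. At alpha 0.05 that holds only without baseline adjustment: at r = 0.5 the figure is 79.9%, and at r = 0.7 it is 92%. Nor should the 27% or 21% be taken as the trial's true power. They come from an unpaired analysis that the SAP does not name, whereas section H runs one ADAPT+ and one EUC cohort in each cycle, which would allow other analyses.

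Finally, this is a small feasibility study, its size follows from cohorts, sites and cycles, and section K itself leaves outcome evaluation to a larger trial. All of that limits the consequence. It does not supply the missing inputs, and it sits awkwardly beside a sentence saying that the trial is powered.

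**Conclusion.** The power claim is incompletely specified and cannot be verified. Read as a comparison of the randomized arms, it is not supported at the stated minimum: about 40% power two-sided or 52% one-sided, assuming alpha 0.05, an unadjusted t-test, no attrition and no cohort effect. Even counting parents and children as independent does not reach 80% unless a baseline adjustment is added that the SAP does not plan. Allocation by whole cohorts and attrition would lower these figures by an amount that the documents do not let us fix.

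The omission is certain. The between-arm reading is plausible but not the only one. Severity is minor, because no decision rule uses the figure and the study is a feasibility pilot.

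**What to change.** Change one sentence in section K, in one of two ways.

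- **Delete the power claim** and justify 48 to 60 pairs as a feasibility sample: 8 to 10 pairs × 2 sites × 3 cycles.
- **Restate it** with the contrast, the number per role per arm (24 at the minimum), alpha, sidedness, test, any baseline adjustment, and the detectable effect allowing for cohorts over a labelled range of assumed ICC and attrition.

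If a pooled pre-post change was meant, say so and do not call it power of the randomized trial. In either case, do not count parents and children as 96 independent observations, and report outcome contrasts as estimates with confidence intervals, which section K already intends to provide.

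The sample size, allocation and data collection do not change. The cost is a less favourable stated figure.
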